4 STUDY POPULATION

4.1 INCLUSION CRITERIA

Eligibility criteria include adults who are >18 years old, insufficiently active (engaging in moderate-vigorous physical activity< 60 minutes per week), residents of participating rural Black Belt (Marengo, Choctaw, Sumter, Hale, Greene, Dallas) counties, BMI 18.5-45, no serious medical condition that would make physical activity unsafe (history of heart disease, myocardial infarction, angina, stroke, or orthopedic conditions which limit mobility), not planning to move from the area within the next 18 months, able to speak and read English, willing to be randomized to either study arm and adhere to study protocol, and able to regularly access a telephone (own a cell phone or work/home landline) to complete IVR calls.

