Secondary measures at baseline, 6 months, and 12 months were included in the cost-effectiveness analyses. We will use a health care utilization survey that captures information on physician and emergency room visits and hospitalizations; the EuroQol-5 Dimension, which estimates utility weights to estimate quality-adjusted life years (QALYs); and a set of questions to measure time spent and expenses related to participation and time devoted to physical activity.

An 18-item measure adapted from similar past studies will assess participant satisfaction with the DIAL intervention and request suggestions for program improvement at 12 and 18 months. Finally, a similar survey will be administered at 18 months to the rural county coordinators to

examine stakeholders' perspectives on acceptability, barriers to and facilitators of implementation, and sustainability of the DIAL intervention in the Deep South.

The research staff will complete the three components of the Rural Active Living Assessment (RALA) for each county at baseline. This assessment consists of the street segment assessment to evaluate factors such as walkability, safety features, and terrain of individual, specific street segments; the town-wide assessment that examines community characteristics such as population, total area, and the presence of recreation activities; and finally, the program and policy assessment, which identifies community programs and policies that support physical activity.

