An 18-item measure adapted from similar past studies will assess participant satisfaction with the DIAL intervention and request suggestions for program improvement at 12 and 18 months. Finally, a similar survey will be administered at 18 months to the rural county coordinators to examine stakeholders' perspectives on acceptability, barriers to and facilitators of implementation, and sustainability of the DIAL intervention in the Deep South.

The research staff will complete the three components of the Rural Active Living Assessment (RALA) for each county at baseline. This assessment consists of the street segment assessment to evaluate factors such as walkability, safety features, and terrain of individual, specific street segments; the town-wide assessment that examines community characteristics such as population, total area, and the presence of recreation activities; and finally, the program and policy assessment, which identifies community programs and policies that support physical activity. These tools have been successfully used in similar past studies conducted by our research team in the Deep South.

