8.3.2 ANALYSIS OF THE PRIMARY EFFICACY ENDPOINT(S)

The primary method of analysis for physical activity, anthropometrics, and psychosocial measures, all of which will be measured at baseline, 6 months, 12 months, and 18 months, will be mixed model repeated measures analyses. Other general linear mixed model techniques may also be used. These analyses will allow us to examine changes from baseline to follow-up (within-group changes) and differences between the study groups simultaneously, while also accounting for the group-by-time interaction as well as any covariates and interactions that are of scientific interest. An appropriate covariance matrix (eg, autoregressive or unstructured) will be selected based on the final data. The Tukey-Kramer multiple comparisons test will be used to determine specific pairwise differences for statistically significant main effects. Some of these models will include the stratification variable of county and confounding variables (as covariates) such as the baseline BMI category, age, gender, and education level. Some of the models that include physical activity as the dependent variable will be adjusted for wear time. Study variables that will be analyzed using these techniques include the change in minutes of moderate-to-vigorous physical activity. Pearson correlation analysis will be performed to assess the relationship between self-reported and measured physical activity.

Distributions of the aforementioned continuous variables will be examined for normality using box plots, normal probability plots, and the Kolmogorov-Smirnov test. Variables that are determined to deviate from a normal distribution will be log-transformed before statistical testing. Nonparametric tests (eg, the Wilcoxon rank-sum test and the Wilcoxon signed-rank test) may also be used to analyze nonnormally distributed data.

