8.3.3 ANALYSIS OF THE SECONDARY ENDPOINT(S)

We will investigate potential mediators of the intervention effect (*social support*) using a multiple mediation approach in SPSS, in which all potential mediators are tested simultaneously, using a product of the coefficients method with bootstrapped SEs (5000 samples with replacement). The interest is in estimating the path coefficients, effect sizes, and CIs rather than strict hypothesis testing.

Potential moderators and interactions will be assessed as follows. A variable will be considered a moderator if evidence exists of either qualitative or quantitative interaction with the intervention. We will use a similar analytic approach as in the primary aims; models will include the main effects of intervention (DIAL intervention vs control), the potential moderator (eg, education and neighborhood and environmental features), and the interaction between the two. Evidence of moderation exists if the coefficient of the interaction term is statistically different from zero.

Descriptive analyses of quantitative stakeholder acceptability survey items and content analyses of open-ended items from stakeholder acceptability surveys and focus group transcripts will be conducted to inform future efforts toward sustainability and large-scale dissemination in rural counties.

If, as hypothesized, the DIAL intervention results in significantly greater increases in moderate-to-vigorous physical activity minutes, we will conduct a within-trial cost-effectiveness analysis to determine if the DIAL intervention is cost-effective compared with no active intervention. Perspectives will be those of the health care sector, participants, and society. The time frame will be 6 months. We will estimate the DIAL implementation costs and participants' medical and other costs that may be affected. Effectiveness will be measured by the change in moderate-to-vigorous physical activity minutes and QALY.

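### Environmental moderators appear to be scored for only six counties, yet moderation is declared from a participant-level interaction with no county-by-arm error term

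*Combined protocol and SAP*

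**What the plan says.** **Moderators and model.** Section 8.3.3 says of moderation: "We will use a similar analytic approach as in the primary aims". The models contain the intervention, "the potential moderator (eg, education and neighborhood and environmental features), and the interaction between the two". The decision rule is "Evidence of moderation exists if the coefficient of the interaction term is statistically different from zero". Section 8.3.1 makes all tests two-sided at P<.05.

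**Environment measure.** Section 7.1, repeated in 8.1, says: "The research staff will complete the three components of the Rural Active Living Assessment (RALA) for each county at baseline". No other measure of the environment is described. One RALA component looks at features such as the "terrain of individual, specific street segments" and another is town-wide, but no rule links segments or towns to a participant.

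**Counties.** Section 4.1 admits "residents of participating rural Black Belt (Marengo, Choctaw, Sumter, Hale, Greene, Dallas) counties", which makes six.

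**Role of county.** In section 8.3.2 county is a covariate in some models only. No random county effect, county-by-arm term or small-sample df method is given. The section adds: "Other general linear mixed model techniques may also be used".

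**Design.** Section 5.2 randomizes individuals, stratified by county and BMI group. The synopsis places moderators under the exploratory aims; section 3.1 lists them with the secondary endpoints.

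**The concern.** A feature that takes one value per county carries information from six units, however many people live in them. An arm-by-score coefficient in a participant-level model is judged against participant-level residual variation, with a critical value near 1.97. That is adequate only if, apart from the score, DIAL works equally well in every county.

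There is a reason to doubt this. Section 5.1.1 gives local coordinators part of the delivery, including help with barriers and walking groups, so differences in delivery follow county lines. With six counties, such differences will line up with a RALA score by chance fairly often, and the stated model has nothing to absorb them. At stake is a claim that a feature of the environment modifies the effect, when the data show only that some counties did better than others.

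**Working it through.** **1. The plan's own figure.** Section 8.2 assumes a difference of 35 minutes, SD 90, two-sided 5% and 80% power, and gives 105 per arm. Normal approximation: 2 × (1.96 + 0.84)² × 90² / 35² ≈ 104 per arm. The noncentral t gives 104.8, hence 105, with power 80.1%. The figure reproduces, so SD 90 is used below for the 6-month change.

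**2. Inputs.** There are 210 evaluable participants (8.2) in six counties (4.1). With an even spread, which is an assumption, that is 35 per county and 17.5 per arm. The between-county SD of DIAL's true effect, τ, is not in the documents. It is varied from 0 to 35 minutes per week, the upper end being the whole planned effect.

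**3. Formula.** The sampling variance of one county's arm difference is v = 2 × 90² / 17.5 = 925.7, so its SE is 30.4 minutes. If τ is unrelated to the score, the true variance of the interaction estimate is (v + τ²)/v times the variance the participant-level model assumes. The chance of a false declaration is 2 × [1 − Φ(1.96 / √(1 + τ²/v))].

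Example, τ = 17.5: 1 + 306.25/925.7 = 1.331; 1.96/√1.331 = 1.70; two-sided probability 8.9%.

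**4. Results.** The simulations used 4,000 trials per setting, with a single 6-month change per person in place of the repeated-measures model, and county as a fixed covariate. The unequal case had counties of 70, 50, 30, 24, 20 and 16. The county-level test regresses the six arm differences on the score (4 df).

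| τ (assumed) | 1 + τ²/v | Participant-level test, formula | Simulated, equal counties | Simulated, unequal counties | County-level test, equal / unequal |
|---|---|---|---|---|---|
| 0 | 1.000 | 5.0% | 4.8% | 4.8% | 4.8% / 5.3% |
| 10 | 1.108 | 6.3% | 6.0% | 6.4% | 4.5% / 5.2% |
| 17.5 | 1.331 | 8.9% | 8.9% | 9.3% | 5.0% / 5.1% |
| 25 | 1.675 | 13.0% | not run | not run | not run |
| 35 | 2.323 | 19.9% | 18.7% | 20.6% | 5.1% / 4.5% |

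All 240 enrolled (40 per county) would give 6.4%, 9.5%, 14.1% and 21.6% at τ = 10, 17.5, 25 and 35 by the formula. Leaving county out of the model changed the simulated rates little (18.1% in place of 18.7% at τ = 35 with equal counties).

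**5. County means alone.** With county means varying (SD 20) but τ = 0, the participant-level test rejected in 5.4% of trials with county in the model and 5.1% without. Differences in average activity do no harm; only differences in the effect do.

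**6. What six counties can show.** Scale the score to SD 1 across the six counties (divisor 6). At τ = 0 the SE of the interaction is 30.4/√6 = 12.4 minutes. With 4 df the critical value is 2.776, so the 95% interval is about ±34.5 minutes per SD of the score, nearly the whole planned effect. The participant-level interval would be about ±24.5 (1.97 × 12.4).

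**7. Aliasing.** If county enters as a fixed categorical effect, the main effect of a county-level score, which 8.3.3 requires, is aliased with it. Six county effects also allow at most five county-level interactions jointly. Neither point depends on τ.

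**The case against.** - **Degrees of freedom.** A reader might infer that the plan prescribes participant-level df. It states none, and it leaves room for other mixed models. The participant-level reading is what a default fit of the described model would give. The objection stands as to certainty, but an open option does not supply the missing error term.
- **Inflation is not automatic.** A reader might infer that false moderation findings will be too frequent whatever happens. The documents do not support that. Randomization within county cancels county differences in mean activity, and step 5 confirms it. Inflation needs the effect itself to vary.
- **Size of the variation.** A τ of 35 is extreme: with a normal distribution around a mean of 35, Φ(−35/35) = 16% of counties would have a negative true effect. At τ = 17.5 the share is Φ(−2) = 2%. The automated call schedule (5.1.2) and the scripted manuals and weekly system audits (5.3) should limit variation. This favours the lower part of the table without fixing a value.
- **Six values is an inference.** RALA has street-segment and town-wide parts, so scores below county level are possible. No assignment rule is given, and completion per county is what the text describes.
- **Use of the results.** A reader might infer that the moderator findings are meant to guide dissemination. In 8.3.3 the dissemination sentence concerns stakeholder surveys and focus-group transcripts, and 3.1 ties dissemination to coordinator surveys and interviews. Moderators are a separate, exploratory aim, and no primary conclusion rests on them.

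**Conclusion.** The concern holds in a conditional form. As described, the environmental moderators appear to vary only between six counties, and the stated rule judges them in a model that cannot separate the score from other county differences in DIAL's effect.

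If the effect varies modestly (τ of 10 to 17.5 minutes), the nominal 5% becomes about 6% to 9%. It reaches about 20% only when τ is as large as the planned effect, and stays near 5% when τ is zero. These figures rest on an assumed τ, SD 90, 35 evaluable participants per county, and a score assigned at county level. Unequal county sizes change them little.

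Education, an individual-level moderator, is not affected, and neither is the primary comparison. This is a minor point in an exploratory aim, but it concerns a written decision rule that can be replaced at little cost.

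**What to change.** Amend section 8.3.3 as follows:

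1. State how each RALA component is scored and assigned to a participant: by county, town or street segment.
2. For any score assigned at county level, estimate DIAL's effect in each county and regress the six effects on the score (4 df). Alternatively, add a random county-by-arm effect with a small-sample df method.
3. Report these results as estimates with intervals, labelled exploratory, and do not apply the significance rule to them. Section 8.3.3 already takes this stance for mediators.
4. Say whether county is also a fixed covariate. If it is, note that the main effect of a county-level score is then not estimable.
5. Keep the stated rule for individual-level moderators such as education.

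The cost is SAP wording; no new data are needed. There will be little power to call any county feature a moderator, as the interval of about ±34.5 minutes shows. With six counties, a random county-by-arm variance will also be poorly estimated. The change makes the uncertainty honest but does not remove confounding: a coordinator difference that tracks a RALA score would still look like an effect of that score, and the report should say so.

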8.3.4 SAFETY ANALYSES

This study involves an educational intervention aimed at promoting physical activity. Thus, it is a minimal risk level study that dictates annual review by the UAB Institutional Review for Human Subjects (IRB) -Expedited Review, as the probability and magnitude of harm or discomfort anticipated in the research are not greater in and of themselves than those ordinarily encountered in daily life or during the performance of routine physical or psychological examinations or tests. Moreover, this study will receive annual review by the University of Alabama at Birmingham Clinical Trials Review Committee (CTRC) for scientific progress and IRB compliance. Note that research staff will be capturing adverse events that are called into the toll-free study number, as well as captured from IVR calls and at in person assessments. This data and safety monitoring plan has been developed to ensure and maintain the scientific standard and protect the safety of the participants. [name] is primarily responsible for the plan with oversight from her Co-Investigators, Drs. [name], [name], [name], [name], and [name], with consultation/quidance from the study physician, [name]. The plan calls for monitoring of adverse events, ensuring that the recruitment goals are on target, and protecting data/confidentiality. Based on our preliminary work, and on a vast literature on moderate intensity physical activity, we anticipate that our intervention will be low risk and that negative side effects will be rare. Nonetheless, we will have multiple levels of data safety and monitoring.

The adverse event reporting protocol includes several steps. In each IVR call, participants will be asked if they have experienced any physical symptoms or complaints that could interfere with their PA program. If they respond 'yes', they are told to stop exercising and contact their personal physician to discuss the health issues further. The IVR system will then prompt staff to follow up with a telephone call to the participant within 48 hours and discontinue PA intervention until physician clearance is provided. On a quarterly basis (by mail at 3, 9, 15 months and in person at 6, 12, and 18 month assessments), participants will be asked if they have experienced any physical symptoms or complaints that could interfere with their physical activity program, any serious health events that caused them to seek medical attention, and if any of these resulted in hospitalizations overnight. Details of these events will be recorded. All participants will be instructed to seek immediate care (through their physicians or emergency room) if problems occur. A toll-free number will be provided for communicating these issues with study staff to assure timely response and submission of regulatory work that is required through the UAB IRB. Instructions on the importance of reporting adverse events through the toll-free study number and surveys etc will be included on all study binders, emails, and cover letters that accompany the intervention measures and materials.

All health occurrences will be recorded and regularly reviewed by the study team, including [name] (study physician), and the UAB Institutional Review Board Office. The study staff will record all reported events in the adverse event log (including the participant name, date, and event description; minority status and gender also will be included in these reports to allow for detection of differential effects) and immediately notify the PI ([name]) of any unanticipated serious events (including deaths should they occur) that potentially jeopardize participation in the study. [name] will consult with [name] (study physician) on the action that should be taken. This communication will occur within 24 hours (for an unanticipated study death), and 5 business days for an unanticipated serious event. This action and date of implementation also will be recorded in the adverse event log. All serious health events will be reported within 3 business days to the UAB IRB. The research team will participate quarterly in classifying any reported events as "serious" or "non-serious" as well as "non-attributable,"

"possibly attributable" or "attributable" to the intervention. In completing this exercise, the team will be blinded to arm status.

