staff. After all assessment measures are complete, participants will be randomly assigned to a group. Intervention participants will receive orientation to the IVR system and begin the physical activity intervention and the Waitlist Control participants will be encouraged to maintain their normal routine until 6 month assessments. At 6-, 12-, and 18- months, participants will repeat accelerometer wear protocols, 7-Day Physical Activity Recall interviews (by phone), and inperson assessment visits (weight, waist circumference, 2 Minute Step Test, psychosocial surveys) with local staff. Psychosocial surveys will also be distributed at 3-months to a assess potential mediators/ moderators of treatment efficacy. Participants will also complete surveys and exit interviews to assess program satisfaction and solicit feedback for improvement (at 12 months for the intervention arm and 18 months for the waitlist control arm). The wait-control group will be offered the 12 month DIAL intervention (same as intervention arm) after the 6 month assessment.

Throughout the project period, UAB research staff and Office of Community Outreach and Engagement county coordinators will report study progress via weekly emails and Zoom meetings. Surveys and in-depth qualitative interviews with participating Office of Community Outreach and Engagement county coordinators will be held to reflect on barriers and facilitators to implementing IVR-supported cancer prevention interventions in rural Black Belt counties, as well as issues surrounding sustainability and future large scale dissemination.

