7.2 ADVERSE EVENTS AND SERIOUS ADVERSE EVENTS

7.2.1 DEFINITION OF ADVERSE EVENTS (AE)

Adverse event means any untoward medical occurrence associated with the use of an intervention in humans, whether or not considered intervention-related (21 CFR 312.32 (a)).

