7.2.4 TIME PERIOD AND FREQUENCY FOR EVENT ASSESSMENT AND FOLLOW-UP

The occurrence of an adverse event (AE) or serious adverse event (SAE) may come to the attention of study personnel during study visits and interviews of a study subject presenting for medical care, or upon review by a study monitor.

All AEs including local and systemic reactions not meeting the criteria for SAEs will be captured on the appropriate case report form (CRF). Information to be collected includes event description, time of onset, clinician's assessment of severity, relationship to study (assessed only by those with the training and authority to make a diagnosis), and time of resolution/stabilization of the event. All AEs occurring while on study must be documented appropriately regardless of relationship. All AEs will be followed to adequate resolution.

Any medical condition that is present at the time that the subject is screened will be considered as baseline and not reported as an AE. However, if the study subject's condition deteriorates at any time during the study, it will be recorded as an AE.

Changes in the severity of an AE will be documented to allow an assessment of the duration of the event at each level of severity to be performed. AEs characterized as intermittent require documentation of onset and duration of each episode.

The Study Coordinator will record all reportable events with start dates occurring any time after informed consent is obtained until 7 (for non-serious AEs) or 30 days (for SAEs) after the last day of study participation. At each study visit, the Study Coordinator will inquire about the occurrence of AE/SAEs since the last visit. Events will be followed for outcome information until resolution or stabilization.

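### The quarterly non-serious symptom question in 8.3.4 presupposes an activity programme, so events in people off the programme, including the wait-list arm at months 3 and 6, may be under-ascertained

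*Combined protocol and SAP*

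**What the plan says.** Section 8.3.4 sets the quarterly schedule: "On a quarterly basis (by mail at 3, 9, 15 months and in person at 6, 12, and 18 month assessments". At each contact, "participants will be asked if they have experienced any physical symptoms or complaints that could interfere with their physical activity program". The same sentence also asks about "any serious health events that caused them to seek medical attention, and if any of these resulted in hospitalizations overnight". Each IVR call carries a symptom prompt tied to the programme in the same way.

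On who has a programme and when, Section 3.1 says that "Waitlist Control participants will be encouraged to maintain their normal routine until 6 month assessments", and that "The wait-control group will be offered the 12 month DIAL intervention (same as intervention arm) after the 6 month assessment". Sections 1.1 and 5.1 give DIAL a length of 12 months.

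On what should be recorded, Section 7.2.1 defines an adverse event as "any untoward medical occurrence associated with the use of an intervention in humans, whether or not considered intervention-related". Section 7.2.4 adds that "All AEs occurring while on study must be documented appropriately regardless of relationship" and that "At each study visit, the Study Coordinator will inquire about the occurrence of AE/SAEs since the last visit". Section 8.3.4 also provides a toll-free number and capture at in-person assessments. It has seriousness and attribution classified blind to arm. It states no between-arm event rate, ratio or test.

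**The concern.** The harms that Section 2.3.1 expects are mostly minor: discomfort, sprains, and other soft-tissue or bone injuries. At the quarterly contacts only the symptom question reaches events of that kind, since the other parts concern serious events and hospitalisation. Taken literally, a wait-list participant with a sprain at month 3 can truthfully answer no, because there is no programme for the sprain to interfere with. A DIAL participant with the same sprain would answer yes.

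Months 0-6 are the only period with an untreated comparator. If the question used in both arms elicits events differently by arm, a by-arm listing of minor events for that period cannot be read at face value. Restricting the listing to shared contacts would not fully cure this, because the shared question is itself the source of the difference. Blinded classification cannot recover events that were never elicited. The plan's expectation of rare side effects would then be hard to support or refute with its own comparator.

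**Working it through.** The plan states no adverse event rate or safety calculation, so there is no figure to reproduce. The check sets the sections side by side and then gives an illustration on stated assumptions.

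**1. Who is on the programme at each quarterly contact** (8.3.4 for schedule, 3.1 and 5.1 for programme timing, 7.2.4 for the visit enquiry)

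| Month | Mode | DIAL arm on programme | Wait-list arm on programme | General visit enquiry |
|---|---|---|---|---|
| 3 | mail | yes | no | no |
| 6 | in person | yes | no (offer comes after this assessment) | yes |
| 9 | mail | yes | if taken up | no |
| 12 | in person | yes (to its end) | if taken up | yes |
| 15 | mail | no | if taken up | no |
| 18 | in person | no | if taken up (to its end) | yes |

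The question lacks a referent at two of six contacts in each arm: months 3 and 6 for wait-list, months 15 and 18 for DIAL. Only the first pair falls in the controlled period.

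**2. Routes open to a wait-list participant with a non-serious event before month 6**

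- Month-3 mailing: the programme-linked question only.
- Month-6 visit: the programme-linked question plus the general enquiry in 7.2.4. That enquiry covers the time since the last visit, so it reaches back to baseline, with up to six months' recall.
- Toll-free number: available throughout, but it depends on the participant calling.
- Monthly virtual events (4.4): contact takes place, but no adverse event question is attached.
- IVR prompts: none.

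**3. Illustrative size.** Assume equal true rates and full capture on DIAL. Let u be the share of wait-list events captured by programme-neutral routes, and s the share of the remainder reported despite the wording. The apparent DIAL-to-wait-list ratio is

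ratio = 1 / [u + (1 − u)s]

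For example, u = 0.5 and s = 0.75 give 1 / (0.5 + 0.375) = 1.14.

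| u | s = 0 | s = 0.5 | s = 0.75 | s = 1 |
|---|---|---|---|---|
| 0.50 | 2.00 | 1.33 | 1.14 | 1.00 |
| 0.25 | 4.00 | 1.60 | 1.23 | 1.00 |
| 0.10 | 10.0 | 1.82 | 1.29 | 1.00 |

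Both u and s are assumptions; the documents give neither. The low-u, low-s corner gives little credit to the month-6 enquiry and should be read as an extreme.

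**4. The IVR asymmetry.** Section 5.1.2 schedules daily calls for three months and two a week in months 4-6: 13 × 7 + 13 × 2 = 91 + 26 = 117 scheduled symptom prompts by month 6 on DIAL, against none on wait-list. Suppose the common contacts were worded neutrally and captured a share q of events in both arms, and IVR picked up a share v of the rest on DIAL. The ratio would be [1 − (1 − q)(1 − v)] / q. With q = 0.7 and v = 0.6 (assumed), it is (1 − 0.3 × 0.4) / 0.7 = 0.88 / 0.7 = 1.26. Rewording the quarterly question alone therefore does not equalise ascertainment.

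**The case against.** The strongest reply is that the plan has other ways to find control-arm events. The serious-event and hospitalisation questions make no reference to a programme. The general enquiry at the month-6 visit covers the whole of months 0-6 in both arms, and all events must be documented whatever their relationship. This stands. A reader might infer that wait-list events cannot be measured at all, and the documents contradict that. What remains is weaker ascertainment of non-serious events: no neutral prompt at month 3, then one long recall at month 6.

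A second reply is that no between-arm comparison is planned, and this also stands. A reader might infer that DIAL's relative rate is inflated, or work out the chance of a falsely significant excess. Both would describe an analysis that 8.3.4 does not contain, using reporting fractions that the documents do not give. Even the direction is not established, since asking only about complaints that could interfere may also screen out minor ones on DIAL.

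Third, over 18 months the mismatch balances. If the wait-list arm takes up the offer, each arm has four contacts on programme and two off. A whole-study tally would not systematically favour one arm, but neither would it isolate the period with an untreated comparator.

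Fourth, 8.3.4 paraphrases the question, and the mailed form is not in the documents. It may read more neutrally, which is a reason to check it.

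Finally, 7.2.1 ties an adverse event to use of an intervention, so the conflict with that definition is not clean. The firmer basis for neutral elicitation is 7.2.4.

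**Conclusion.** The concern holds in a limited form. As described in 8.3.4, the quarterly symptom question fits people on DIAL and fits poorly those off it, so non-serious events may be under-ascertained off the programme. The gap is clearest at the month-3 mailing and is partly closed at month 6. Any by-arm description of non-serious events in months 0-6 could overstate DIAL's relative frequency.

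The size cannot be derived from the documents. On the assumptions shown, the apparent ratio is 1.00 if the wording suppresses nothing. It is 1.14 if half of wait-list events reach neutral routes and three quarters of the rest are still reported, and 2.00 if none of the rest are. These figures assume equal true rates and full capture on DIAL. Serious events are not affected by this wording. The difference in IVR prompting, 117 scheduled against none by month 6, is a separate and probably larger source of unequal ascertainment and needs its own handling.

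**What to change.** In 8.3.4, replace the first quarterly item with one asked identically of every participant at every contact: any new or worsened symptom, injury or health problem since the last contact. Follow it with a separate question on whether the problem limited usual activity or exercise, which keeps the information the present wording seeks. Bring the mailed and in-person forms into line. Keep the programme-specific wording for the IVR calls.

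State that any by-arm summary of non-serious events for months 0-6 will use only events captured through contacts common to both arms, and that IVR-captured events will be reported separately.

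The cost is one form revision and an IRB amendment, and more minor, unrelated events will be logged in both arms. If participants have already answered the existing question, record the date of the change so that the two sets of responses are not pooled without comment.
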